4.7 Inference

For our core analyses, we will use heteroskedasticity-robust standard errors. We will check for additional statistical robustness following the approaches outlined in Section 5 of the Supplementary Appendix of [this paper](#).

5. Funding and Human Subjects Review

Facebook is supplying sufficient ad credits to fund the campaign. The IRB at MIT is serving as the primary institution of record and has entered into a reliance agreement with Harvard, Stanford, Massachusetts General Hospital, and Yale.

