2.5 Treatment Assignment

The counties in the study sample were randomized into three treatment groups and a control group: 1) a “direct” messaging group (T1), 2) a “friends” messaging group (T2), 3) a “gossips” messaging group (T3), and 4) a control group which did not receive any Facebook ads from us.

Randomization was conducted at the county level. County-level randomization was stratified by three characteristics: 1) state, 2) political leaning (according to 2020 election results), and 3) baseline vaccination rates. For political leaning, counties were divided into below- and above- median GOP vote in the 2020 presidential election. For baseline vaccination rates, counties were divided into above- and below-median percentage of the population that had received the 1st dose of Covid-19 vaccine.

After stratifying on these three variables, strata were adjusted so that no stratum was smaller than 9 counties. Strata with fewer than nine counties were dissolved by baseline percentage of population with first dose of vaccine. For the three states (South Carolina, Michigan, and Wyoming) where this does not result in strata that have at least nine counties, we dissolve instead by baseline GOP vote share. In total, this left us with 47 strata.

Exceptions: County-level GOP votes were not available for Alaska, and so this stratification variable was used for the other 18 states in the sample only.

Out of the 1,397 counties which fit the eligibility criteria for the experiment, we assigned 468 counties to the control group, 310 counties to T1 (“direct” messaging) treatment, 309 counties to T2 (“friends” messaging), and 310 counties to T3 (“gossips” messaging).

3. Hypotheses

Primary hypotheses:

1. Do the ads affect the new Covid-19 vaccinations in treated areas?
 - 1st dose of vaccine
 - 2nd dose/completed vaccination
 - Booster shots
2. Which type of messaging (“direct,” “friends,” or “gossips”) is most effective at driving engagement and shares of vaccine-related content, as well as new vaccinations?

3. Is myth- or question-based messaging more effective at eliciting engagement with vaccine-related content?

Secondary hypotheses:

4. Do the ads affect Covid-19 cases, hospitalizations, or symptoms in treated areas?
5. Do the ads spill over onto other areas that are connected to the treatment counties?
 - Behavioral spillovers: new vaccinations
 - Covid-19 case, hospitalization, symptom impacts

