4.1 Primary Outcomes

1. **Covid-19 vaccinations:** this includes 1st doses, 2nd doses/completed vaccination, and booster shots when available. These data are available at the county level.

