4.4 Regression Analysis

1. Effects of treatment on county-level outcomes (Covid-19 vaccinations, content engagement, other behavioral or survey outcomes):

- (a) Main analysis: $Y_{ct} = \alpha_t + \gamma_c + \beta_1 Direct_{ct} + \beta_2 Friends_{ct} + \beta_3 Gossips_{ct} + \delta Y_{c0} + \epsilon_{ct}$
 - Y_{c0} is a baseline measure of the outcome
 - *Direct, Friends* and *Gossips* are the three treatment groups. Treatment is assigned at the county level. We may also pool together friends and gossips, or all three treatment groups in some specifications.
- (b) Heterogeneous effects of treatment: $Y_{ct} = \alpha_t + \gamma_c + \beta_1 X_{ct} + \beta_2 Treat_{ct} + \beta_3 Treat_{ct}X_{ct} + \epsilon_{ct}$
 - We plan to explore heterogeneity along the following dimensions:
 - Political leaning (red/blue) – this was a stratification variable
 - Baseline vaccination rates – we stratified on baseline population percentage with 1st dose of vaccine
 - Percentage white/non-white
 - Relevant vaccine mandates
 - Prior/baseline infection rates
 - Urban vs rural

We may look at heterogeneity in specifications which consider each treatment group separately, as well as specifications which pool together treatment groups.

- (c) Distributional impacts using quantile regression
 - We may repeat the exercises above with quantile regressions.
- (d) Do people who visit the study website from different treatment groups click on different content (e.g. vaccine-related videos)? For example, do website visitors respond to myth vs fact videos differentially by treatment group?

2. Comparing the efficacy of myth- vs question-based messaging

- (a) $Y_{ict} = \alpha_t + \gamma_c + \beta \mathbb{1}(Myth_{ict}) + \epsilon_{ict}$
 - Y_{ict} stands for engagement-related outcomes such as video views, website visits, and video shares
 - We will examine myth- vs question-based messaging at both the Facebook ad level and at the website level. (The videos vary in whether they are myth- or question-based both in the Facebook ads which are served to users, as well as in the videos which are visible to website visitors.)

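### Core standard errors are heteroskedasticity-robust only, with no clustering by county, and are too small in some of the multi-row county layouts that the plan leaves open

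*Combined protocol and SAP*

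**What the plan says.** Section 4.7 sets the rule for the main results: "For our core analyses, we will use heteroskedasticity-robust standard errors". It then refers to further robustness checks in the appendix of a linked paper, described as additional. Clustering is not mentioned anywhere in the plan.

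Section 2.5 states "Randomization was conducted at the county level", and Section 4.4 repeats "Treatment is assigned at the county level". The primary outcome is vaccination, with the first hypothesis in Section 3 put as "Do the ads affect the new Covid-19 vaccinations in treated areas"; Section 4.1 adds "These data are available at the county level".

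The main model, Section 4.4 item 1(a), gives the outcome and all three treatment indicators both a county and a time index. It has a time term, a term indexed by county (gamma_c) and a covariate Y_c0 that "is a baseline measure of the outcome". The plan does not say how many periods enter, whether pre-launch rows are used, or whether gamma_c is a full set of county effects. Section 2.3 gives only the campaign length, five weeks.

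**The concern.** Heteroskedasticity-robust errors allow unequal variances but take every row as independent. Rows from one county share a single treatment assignment. If their errors are positively correlated, extra rows add less information than the formula credits. The standard errors of beta1, beta2 and beta3 are then too small, the intervals too short, and a campaign with no effect is declared effective more often than 5% of the time. This bears on the primary vaccination outcome.

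The printed model points towards several rows per county, since a time effect has no use with one time point. The term gamma_c does not settle the matter. If it is a full county effect, Y_c0 and the state effects and baseline rates listed as candidate controls in Section 4.6 would be absorbed by it, so a model without county effects cannot be ruled out. If it is a county effect, serial correlation can still bias the robust errors.

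**Working it through.** The plan states no alpha, power, effect size or within-county correlation, so there is no planned figure to reproduce. The county counts agree: 468 + 310 + 309 + 310 = 1,397 = 1,402 − 5.

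**Inputs from the plan:** 1,397 counties and 47 strata of at least nine (Section 2.5); five campaign weeks (Section 2.3).

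**Assumed:** two-sided 5% test; number of rows per county; within-county correlation r, either AR(1) or constant; individual stratum sizes.

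**Formula.** Let D be the true variance of a treatment coefficient divided by the variance that the robust formula reports. The false-positive rate is 2 × [1 − Φ(1.96/√D)], and robust SE / true SE = 1/√D.

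**Case (i): m post-launch rows, baseline covariate, no county effects.** The pooled baseline slope b is the mean correlation of the m rows with baseline, and the residuals are Y_t − b·Y_c0. Treatment is constant over a county's rows, so D is the sum of all entries of the residual covariance matrix divided by the sum of its diagonal.

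- m = 2, AR(1) r = 0.5: b = (0.5 + 0.25)/2 = 0.375. Residual variances are 0.7656 and 0.9531, covariance 0.3594. D = 1 + 2 × 0.3594/1.7188 = 1.418, giving 10.0%.
- m = 5, constant r = 0.5: after baseline adjustment the residual correlation is (0.5 − 0.25)/(1 − 0.25) = 1/3. D = 1 + 4 × 1/3 = 2.333, giving 19.9%.

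**Case (ii): county and week effects, 5 pre and 5 post rows, AR(1) r = 0.5.** The sum of the 10 × 10 correlation matrix is 26.004 and each 5 × 5 block sums to 11.125. The post-minus-pre contrast has variance proportional to 22.25 − (26.004 − 22.25) = 18.496. The robust formula (HC1, with the degrees-of-freedom factor 10/9) uses (10 − 2.6004) × 10/9 = 8.222. D = 18.496/8.222 = 2.25, giving 19.1%.

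**Simulation.** 4,000 null trials per scenario, with assignment re-drawn within strata at 3:2:2:2, HC1 errors, and the mean rejection rate over beta1 to beta3. Case (i) includes week effects, baseline, strata effects and lasso-selected controls. Simulation error is at most about 0.7 points at 5% and 1.4 points at 30%.

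| Layout, AR(1) 0.2 / 0.5 / 0.8 | Formula, % | Simulated, % |
|---|---|---|
| 2 post rows | 7.2 / 10.0 / 11.9 | 7.5 / 10.2 / 12.4 |
| 3 post rows | 8.3 / 13.6 / 17.8 | 8.3 / 13.5 / 18.3 |
| 5 post rows | 9.4 / 17.8 / 26.3 | 9.3 / 17.3 / 26.5 |
| County effects, 2 pre + 5 post | 7.8 / 12.2 / 16.4 | 7.5 / 11.7 / 16.3 |
| County effects, 5 pre + 5 post | 9.5 / 19.1 / 30.0 | 9.6 / 18.6 / 29.8 |

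Five post rows with constant correlation 0.2 / 0.5: 12.9 / 19.9% by formula, 13.2 / 20.4% simulated. Leaving out strata effects hardly alters the AR(1) five-row result (9.1 / 17.3 / 26.0%). In the inflated cases the robust SE is 0.53 to 0.93 of the clustered SE.

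**Layouts with little or no harm (simulated):** one post-launch row 4.9–5.3%; 1 pre + 1 post with county effects 5.0–5.6%; 1 pre + 5 post with county effects 5.1–6.0%; constant correlation 0.5 with county effects 4.9% (2 + 5) and 4.8% (5 + 5); independent errors 4.6–5.4%.

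**With county clustering:** 4.6–5.8%, except 1.9–4.1% when strata effects are left out.

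A separate simulation of 1,000 null trials per layout gave 10.2 / 18.9 / 31.1% for five post rows, 9.3 / 18.7 / 29.2% for 5 + 5 and 7.1 / 13.0 / 16.5% for 2 + 5. Clustered errors gave 4.0–5.8%. It is higher than the table for five post rows at 0.8; otherwise the agreement is close.

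**The case against.** The strongest reply is that the harm is conditional. A baseline-adjusted regression with one endpoint row per county is a natural use of Y_c0, and robust errors are right for it. That stands: no section says that a harmful layout will be used. But this reading leaves the printed time and county terms without a purpose, and the plan does not commit to it.

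A second reply is that the two harmful cases exclude each other. Case (i) needs gamma_c not to be a county effect. Case (ii) needs it to be one, which makes Y_c0 redundant. This is correct, and each reading strains a printed term. It shows that the model is under-specified, not that the standard errors are safe, because either reading can inflate the error rate.

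Third, the linked appendix may contain clustering or randomisation inference. It cannot be consulted here. Because the plan presents those checks as additional, they would not replace the core standard error.

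Fourth, the percentages rest on assumed row counts and correlations. That also stands; they show a range and do not estimate this trial's error rate.

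One qualification makes matters worse. The 1 pre + 1 post layout with county effects is safe only if the robust formula carries a degrees-of-freedom correction. Without it (HC0), D = 2 and the rate is 2 × [1 − Φ(1.96/√2)] = 16.6%. Section 4.7 names no variant.

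**Conclusion.** The concern holds. The stated rule is adequate with one row per county and, given a degrees-of-freedom correction, adequate or nearly so with one pre-launch row and county effects. It is too liberal with two or more positively correlated post-launch rows without county effects, and with several pre- and several post-launch rows, county effects and serially correlated errors. There the simulated false-positive rate is 7.5% to 29.8% for AR(1) correlations of 0.2 to 0.8, about 1.5 to 6 times nominal. These figures assume 2 to 5 post-launch rows, up to 5 pre-launch rows, and new vaccinations per period as the outcome. The plan does not exclude these layouts, so this should be fixed, although which layout the investigators intend is not known.

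**What to change.** 1. Replace the first sentence of Section 4.7 with: *Standard errors are clustered by county, the unit of randomisation, in every treatment-effect regression with more than one row per county; where the outcome is collapsed to one row per county, heteroskedasticity-robust errors are used.* This also covers the two-row layout, where the choice of robust variant matters.
2. In Section 4.4, state the number of pre- and post-launch periods and whether gamma_c is a full county effect.

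The website comparison of myth and question framing is randomised by visitor and is exempt when it has one row per visitor.

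The cost is one sentence, one line and one software option. In the affected layouts the intervals widen: the clustered SE is about 1.1 to 1.9 times the robust SE (1/0.93 to 1/0.53). If strata effects are left out, clustered tests are conservative (1.9–4.1% instead of 5%). The plan does not promise strata effects, so the authors should weigh this when settling the controls. With one row per county, no result changes.
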